8.1. Analysis Software

Statistical analyses will be performed using SAS Software version 9.3 or higher.

8.2. Withdrawals

Subjects who withdraw from the study prematurely will be considered in all data presentations for which they contribute data.

8.3. Handling of Missing Data

In general, missing data will not be imputed, with a few exceptions. For ANCOVA analysis of changes from baseline to week 16, LOCF will be used in main model in case of missing values (e.g. due to early termination) and in case of switch to the alternate treatment group (as values obtained after the switch will not be included in the analysis).

For missing weight measurements the last available body weight will be used for all calculations related to dosing; in individual patient data listings missing data will however not be replaced by imputed values.

No analyses of the patterns of missing data will be done.

For adverse events the following will be applied:

An Adverse Event (AE) is defined as treatment-emergent, if first onset or worsening is after start of the first infusion of Octagam 10% or placebo.

If the start date and time of an AE are partially or completely missing, the AE will be assumed to be treatment-emergent if it cannot be definitely shown that the AE did not occur or worsen during the treatment emergent period (worst case approach). Missing dates and times will not be replaced.

For medications the following will be applied: A medication will be assumed to be concomitant if it cannot be definitely shown that the medication was not administered during the treatment period as defined in section 8.4 below. Missing dates will not be replaced.

8.4. Derived and Computed Variables

The following derived and computed variables have been initially identified as important for the analysis of the primary and secondary target variables. It is expected that additional variables will be required. The SAP will not be amended for additional variables that are not related to the primary target or key secondary target variables. Any additional derived or computed variables will be identified and documented in the SAS programs that create the analysis files. If the SAP is not amended, further derivations related to primary and secondary target variables will be described in the CSR.

- **Age** will be derived according to the usual definition that a person is n years old until she or he has completed her or his $(n+1)^{\text{th}}$ year of life, using the date of informed consent as the reference date. This is also the definition that will be applied for evaluation of the age related inclusion criteria. [Unit: years]
- **Body Mass Index:** $\text{BMI} = (\text{Body weight}) / \text{Height}^2$ [Unit: kg/m^2]
- The **treatment period** is defined as the period between the day of first treatment with study drug (Octagam or placebo) to the end of the observation period. This will usually be the termination visit.
- **Confirmed Deterioration** is defined as follows:
 - Physician's Global Disease Activity VAS worsening $\geq 2\text{cm}$ and MMT-8 worsening $\geq 20\%$ on 2 consecutive visits,
 - or
 - global extra-muscular activity worsening $\geq 2\text{cm}$ on the MDAAT VAS on 2 consecutive visits,
 - or
 - any 3 of 5 CSM (excluding enzymes) worsening by $\geq 30\%$ on 2 consecutive visits.

For all criteria worsening will be determined by comparing to baseline values (Week 0).

9. Study Subjects and Demographics

9.1. Disposition of Subjects and Withdrawals

All subjects screened for the study will be accounted for. For screening failures only the reasons for not being enrolled in the study will be listed and summarized.

For all subjects enrolled in the study, descriptive summaries of population data will be provided overall and by treatment group; these will include

- The frequency and percent of subjects in each study period and analysis population by country and overall
- Number of subjects enrolled, number of subjects treated, number of completers
- Study withdrawals by reason of withdrawal

9.2. Protocol Deviations

Protocol deviations will be checked on complete data for all subjects prior to defining the analysis populations. The final decision regarding inclusion/exclusion of subjects from the analysis sets will be taken based on data listings and reports during data review meetings before database lock, data release and final analysis, applying the definitions in section 7.

Patients that have baseline scores but no score at 16 Weeks will in general be considered as non-responders in their respective (randomized) treatment group. If a Week 16 score is available, but not within the planned time window of 4 weeks \pm 4 days after the preceding infusion, the decision of whether a particular score can be used for analysis will be made at the data review meeting.

Major and significant protocol deviations will be summarized by type of deviation. Individual subjects with these protocol deviations will be listed.

A dedicated listing will cover the use of forbidden concomitant medication as detailed in the protocol, section 4.2.2.

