4.2.1 Permitted Concomitant Therapy

Previous medications for the treatment of DM (immunosuppressants, corticosteroids or biologicals) must either be

a) washed-out (details see Table 2)

or

b) continued if subject received medication for at least 3 months prior to study enrollment and at a stable dose for at least 4 weeks prior to study enrollment (details see Table 2).

Table 2 specifies which **DM-treatment-related medications** are permitted as concomitant therapy. In addition, the maximally allowed dose which has to remain stable during the First Period is given. If treatment for DM is to be stopped prior to study enrollment, the required washout periods, the period which needs to elapse from discontinuing, can be retrieved from the table.

During the First Period of the study, the dose regime of concomitant therapies should not be changed. During the Extension Period of the study, therapies may be tapered off.

TEE prophylaxis, if deemed necessary by the investigator, is allowed as a precautionary measure and should follow standard of care. Its use must be documented.

The routine use of **premedication** to alleviate potential side effects should be avoided. However, if a subject experiences 2 consecutive infusion-related AEs that are likely to be prevented by premedication, then antipyretics, antihistamines, mild analgesics (acetaminophen/paracetamol or acetylsalicylic acid) or antiemetic drugs are allowed before the following infusions of study drug. The dose of premedication should be held stable during the First Period and its use must be documented.

NSAIDs or opioids are commonly used in DM patients and are therefore allowed. The dose of such medications should be held stable 2 weeks prior to study enrollment and during the First Period. The use of such medication must be documented.

Topical medication, except topical steroids, is allowed. Such medication should be kept stable during the First Phase to avoid interference with the extra-muscular activity, one of the CSM of the primary endpoint.

Physical therapy-directed exercise regimen is allowed if started ≥ 4 weeks prior to randomization and entry into the double-blind treatment period at Visit 2 and kept on a stable schedule, frequency and extent. Any such exercise regimen must be documented.

Table 2: Washout Periods or Dose Limitations for Prior/Concomitant DM-related Medications to be fulfilled prior to randomization

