4.2.2 Forbidden Concomitant Therapy

The following medications or therapies are forbidden during participation in this study:

- Corticosteroids at any dose if given as **premedication** to alleviate potential side effects following Octagam 10% treatment.
- Corticosteroids at doses higher than 20 mg/day prednisone equivalent.
- Other blood or plasma-derived products. Note that subjects will be withdrawn from the study if IgG preparations other than Octagam 10% are administered.
- Plasma exchange procedures.
- Live attenuated vaccines such as measles, rubella, mumps and varicella.
- Any experimental drug.

Table 3 lists further medications that are forbidden, but patients can be included into this study when the respective washout period is considered.

 Table 3: Forbidden Concomitant Medications

Drug	Washout Period (prior to randomization)
Monoclonal antibodies (e.g. adalimumab, infliximab, certolizumab, golimumab, abatacept, tocilizumab)	8 weeks
Rituximab	12 months or 6 months plus normal CD19 count
Cyclophosphamide	3 months
Immunoglobulin G	6 months
Etanercept	4 weeks
Anakinra	2 weeks
Rilanocept	8 weeks
Topical steroids	2 weeks

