5.1. Final Analyses and Reporting

As stated in section 4.1, this study consists of a double-blinded period, followed by an open-label extension period. The blind will however be maintained throughout the complete study to the extent possible; only for subjects who were switched during the first study period and show no further deterioration at Week 16 and for those subjects with confirmed deterioration at Week 16, the decision whether a subject is allowed to continue into the open-label period will imply whether the subject was initially treated with Octagam (Subject has to drop out) or Placebo (Subject continues). Otherwise the blind will not be broken before all subjects have completed the entire study and the final database has been locked and released for analysis according to the applicable standard operating procedures.

This process includes a data review, the identification and classification of any protocol deviations as detailed in section 7, and thus the subject disposition with respect to the analysis populations. All final, planned analyses identified in the protocol and in this SAP will be performed only after the last subject has completed the study, the subject disposition has been agreed and documented, and the final SAP has been approved.

Key statistics and study results will be made available to the study team following database lock and prior to completion of the final CSR by means of tables, figures and listings.

Any, post-hoc, exploratory analyses completed to support planned study analyses, which were not identified in the final SAP, will be documented and reported in the CSR or its appendices. Any results from such unplanned analyses will also be clearly identified in the text of the CSR.

No interim analysis is planned.

6. Sample Size Determination

The sample size calculation is based on the target parameters for the evaluation of the primary endpoint, i.e. the proportions of responders in the Octagam 10% and the placebo group at the end of the 16 week efficacy period (First Period).

A total sample size of 84 subjects is required to show a significant difference in the proportion of responders between Octagam and placebo group with a power of 80%, under the assumption that the true proportions of responders are 0.6 in the Octagam group and 0.3 in the placebo group. The sample size calculation is based on Pearson's chi square test using a two-sided alpha level of 0.05.

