Only significant protocol deviations with the potential to affect the study results significantly, or to invalidate the interpretation of the data obtained, will lead to exclusion of subjects from the PP sets; protocol deviations to be considered will include (but will not be limited to):

- Violations of the study entry criteria
- Withdrawal criteria that developed during the study
- Wrong treatment or incorrect dose
- Prohibited concomitant medication (e.g. IGIV other than Octagam)

Analysis of the safety endpoints will be based on the safety set.

The primary endpoint will be evaluated on basis of the FAS and the PP1 set. The intent-to-treat analysis of the FAS population is considered the primary study outcome, and will be presented first in the statistical output. The primary analysis in the FAS will also include those subjects with significant protocol deviations that are unrelated to disease progression or lack of efficacy, but that have the potential to distort the TIS assessment. This would e.g. include subjects that start an intensive exercise during the first study period.

Because the PP1 set will include all subjects that deteriorated or dropped out for clinical reasons as described above, the difference between the FAS and the PP1 is expected to be small.

All other analyses will be based on the FAS set and/or the appropriate PP set; this will be specified in detail in the list of all tables, figures and listings.

Repetition of an analysis in the PP set might be skipped in case the PP population differs from the FAS by no more than 5 subjects; this does however not apply for the primary endpoint evaluation.

In general baseline tables will summarize data by randomized treatment. Tables by visit will summarize data by randomized treatment, but values obtained after the switch of treatment in first period will be excluded. Adverse events tables will summarize data according to actual treatment at time of AE, i.e. any adverse event will be considered to be associated with the most recent treatment administered, Octagam or Placebo, when summarizing the data. Patients who are switched to the other treatment during the first study period will therefore be considered to be at risk for adverse events in both treatment groups.

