9.3. Demographics and Other Baseline Characteristics

Descriptive summaries of the demographic and other baseline characteristics will be completed for the populations specified below, overall and by treatment group and stratum as applicable; these include:

- Demographics (Age, Gender, Race/Ethnicity, Height, Weight, BMI (calculated))
(SAF, FAS, PP1, PP2)

- Medical History (SAF)

Medical history will be coded with the Medical Dictionary for Regulatory Activities (MedDRA, according to the version specified in the Data Management Plan). Incidences of findings in medical history will be summarized by MedDRA system organ class (SOC) and preferred term (PT)

- Prior and Concomitant Medications (SAF)

Medications will be coded using the WHO Drug Dictionary (according to the version specified in the Data Management Plan). Incidences of prior and concomitant medications will be summarized by ATC level 2 and ATC level 4

- Baseline Physical Examination, including vital signs (SAF)
- Baseline ECG

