10.1. Primary Endpoint

The primary endpoint measure 'response' will be assessed at Week 16 on bases of the TIS score detailed in section 3.2.1: a subject is defined as responder if

- (i) the subject has a TIS score of ≥ 20 points at Week 16 and
- (ii) the subject has not met "Confirmed Deterioration" criteria at 2 consecutive visits as defined in Section 8.4 up to (including) Week 16

Otherwise the subject will be counted as a non-responder in the treatment group he was randomized to Thus subjects who discontinued from the study prior to Week 16 will also be considered as non-responders.

The proportion of responders within both treatment groups will be compared by Cochran-Mantel-Haenszel test, stratified by global disease activity (randomization stratum), using two-sided alpha level of 0.05. The primary analysis will be considered as success if the proportion of responders is significantly higher in the Octagam group compared to the placebo group.

Moreover, an exact two-sided 95% confidence-interval will be constructed for the overall difference in the proportion of responders between Octagam and placebo group, using the 'exact riskdiff' option of the SAS FREQ procedure.

In a sensitivity analysis for the primary endpoint, a logistic regression model will be applied, including global disease activity and further baseline variables as applicable as covariates.

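### A subject whose corticosteroid or Table 2 drug is raised or added before Week 16 can still be a primary responder, and no planned analysis of the primary endpoint counts that subject as a failure

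*SAP*

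**What the plan says.** SAP 10.1 sets two conditions for response. The first is "the subject has a TIS score of ≥ 20 points at Week 16 and"; the second is that confirmed deterioration was not met up to and including Week 16. Subjects who discontinue before Week 16 are non-responders, and SAP 9.2 in general treats a missing Week 16 score the same way. Neither condition refers to concomitant therapy. The one sensitivity analysis named for the primary endpoint is a logistic regression with global disease activity and further baseline variables.

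Protocol 4.2.1 states: "During the First Period of the study, the dose regime of concomitant therapies should not be changed". It also says that the maximum doses in Table 2 have to stay stable in that period. Protocol 4.2.2 is a separate list of forbidden therapy. For systemic corticosteroids it contains premedication use at any dose and "Corticosteroids at doses higher than 20 mg/day prednisone equivalent". It also contains the Table 3 drugs, with no dose threshold.

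SAP 7 excludes significant deviations from PP1. Its open list of examples includes "Prohibited concomitant medication (e.g. IGIV other than Octagam". PP1 expressly keeps subjects who deteriorated and those withdrawn for AEs or insufficient response.

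On reporting, SAP 9.2 plans a table and subject listing of major and significant deviations, and then: "A dedicated listing will cover the use of forbidden concomitant medication as detailed in the protocol, section 4.2.2". SAP 9.3 adds: "Incidences of prior and concomitant medications will be summarized by ATC level 2 and ATC level 4".

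**The concern.** The protocol itself treats background therapy as able to disturb the endpoint: 4.2.1 keeps topical medication stable so that it does not interfere with extra-muscular activity, one of the core set measures. If a subject's DM therapy is stepped up for poor control and the TIS then reaches 20, the improvement is credited to the randomised treatment.

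The confirmed-deterioration rule does not reliably catch this subject. It needs worsening past set thresholds from baseline at two consecutive visits. A subject who merely fails to improve never meets it, and a change made after a first worsening visit could prevent confirmation at the second.

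At stake is whether a reader of the report can tell how many responders in each arm had additional DM therapy, and whether the primary conclusion survives when they are counted as failures.

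**Working it through.** **How each analysis treats the subject.** Take a subject who stays in the study, never meets confirmed deterioration, reaches TIS 20 at Week 16, and had a corticosteroid or Table 2 drug raised or added in the First Period.

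- FAS, primary CMH test: responder.
- PP1: responder if the change is not judged a significant deviation; removed if it is. No rule makes the subject a non-responder.
- Logistic regression: same outcome variable, adjusted for baseline covariates, so it cannot address a change after randomisation.

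Compare a subject withdrawn before Week 16 for insufficient response. That subject is a non-responder in the FAS and is kept as a non-responder in PP1. The same lack of effect leads to failure if the subject leaves, but to response or removal if the subject stays and receives more therapy.

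**Where the change would be reported.**

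- Dedicated listing (SAP 9.2): tied to protocol 4.2.2. It covers Table 3 drugs, premedication steroids and corticosteroids above the stated limit. It does not cover changes within the Table 2 limits.
- Complete deviation list (protocol 4.5): covers the change, because it departs from 4.2.1.
- Deviation table and subject listing (SAP 9.2): only if classed as major or significant, case by case under SAP 7.
- ATC table (SAP 9.3): an added drug adds to the counts, without dose or timing. A dose rise of a drug already taken does not show.
- By-arm output of background dose changes: none specified.

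**Reproducing the plan's sample size.** SAP 6 assumes that "the true proportions of responders are 0.6 in the Octagam group and 0.3 in the placebo group", and says: "The sample size calculation is based on Pearson's chi square test using a two-sided alpha level of 0.05". With mean proportion 0.45:

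n per arm = [1.960·√(2·0.45·0.55) + 0.8416·√(0.60·0.40 + 0.30·0.70)]² / 0.30² = [1.3790 + 0.5646]² / 0.09 = 41.97, so 42 per arm and 84 in total, as stated.

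At the planned enrolment of 94, taken as 47 per arm, power = Φ{[0.30·√47 − 1.960·0.7036] / 0.6708} = Φ(1.010) = 84.4%.

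**Illustration.** Assume that k of 47 would-be non-responders become responders through a change in background therapy. The value of k is assumed; the documents give none. Placebo then reads (14.1 + k)/47 and Octagam (28.2 + k)/47. The calculation uses the same unstratified formula.

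| k | Placebo rate if affected | Octagam rate if affected | Power, placebo only | Power, both arms | Power, Octagam only |
|---|---|---|---|---|---|
| 0 | 0.300 | 0.600 | 84.4% | 84.4% | 84.4% |
| 2 | 0.343 | 0.643 | 71.2% | 84.0% | 92.7% |
| 3 | 0.364 | 0.664 | 63.3% | 84.0% | 95.4% |
| 5 | 0.406 | 0.706 | 46.6% | 84.5% | 98.5% |

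If the same placebo subjects are removed from PP1 instead, the placebo rate is 14.1/(47 − k) = 0.313, 0.320 or 0.336. Counting them as failures gives 0.300. So PP1 does not reproduce the rate obtained when they are counted as failures.

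**The case against.** Several objections have force.

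- **Visibility.** A reader might infer that such changes appear in no planned output. The documents do not support that. A within-limit rise departs from 4.2.1, so it belongs in the complete deviation list of protocol 4.5 and, if classed as major or significant, in the SAP table and subject listing. A restarted drug enters the ATC counts. The full list of tables and listings is deferred to a separate document, so what it contains cannot be judged here. What stands is that the one listing dedicated to medication has the narrower scope, and that no by-arm output of dose changes is specified.
- **Scope of the forbidden list.** It would be wrong to say that 4.2.2 begins only above a corticosteroid dose. It also bans premedication steroids and all Table 3 drugs. The reporting gap is confined to systemic corticosteroids within the limit (other than as premedication) and the other Table 2 drugs.
- **Existing failure routes.** Confirmed deterioration, discontinuation and, in general, a missing Week 16 score already give non-response, and a major deviation triggers a decision on further participation. The subjects left over may be few.
- **Power.** A reader might infer from the placebo-only column that the trial stands to lose power. That column rests on assumed counts placed on one arm. Equal numbers in both arms change almost nothing, and the supportive analysis would not restore power to the primary test in any case.
- **Intention to treat.** Scoring Week 16 response regardless of deviations fits the stated FAS principle. This is a fair reason to leave the primary analysis alone. It is not a reason to omit a supportive analysis.

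**Conclusion.** The point holds in a limited form. A subject who stays in, avoids confirmed deterioration and reaches TIS 20 is a primary responder despite a raised or added corticosteroid or Table 2 drug, and no planned analysis of the primary endpoint counts that subject as a failure. PP1 is inconsistent with its own handling of insufficient response. Within-limit changes depend on general deviation handling to be seen.

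The size and direction of any bias are unknown. Under assumed counts of 2 to 5 per affected arm, power runs from 46.6% (placebo only) to 98.5% (Octagam only), and stays near 84% when both arms are affected equally. These figures assume 47 per arm, the planned response rates and an unstratified normal approximation. They show sensitivity to imbalance between the arms, not an expected loss. Whether any change in background therapy is clinically appropriate is not judged here.

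**What to change.** - **SAP 10.1:** pre-specify a supportive analysis of the primary endpoint in the FAS with the same stratified CMH test. Count as non-responders all subjects who, before the Week 16 assessment, start a new systemic DM drug or exceed their Week 0 dose of a corticosteroid or Table 2 drug. Use the recorded reason to leave out changes made for other conditions.
- **SAP 7:** keep in PP1, as non-responders, subjects whose change was for insufficient response.
- **SAP 9.2:** extend the dedicated listing to First Period changes against protocol 4.2.1, by randomised arm, with dose before and after.

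Define the flag before unblinding. Leave the primary FAS analysis as it is.

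The cost is SAP wording, one derived flag, one extra table and a wider listing. Protocol 4.2 already has concomitant medications recorded in the eCRF throughout the study; that dose, date and reason are captured should be confirmed. The downside is that some flags may reflect changes unrelated to DM where the recorded reason is missing or unclear.
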